HRP-503B – BIOMEDICAL RESEARCH PROTOCOL (2017-1)

Protocol Title: A Very Low Carbohydrate Diet as an Adjunctive Therapy for Youth Type 1 Diabetes

Principal Investigator: [name]

Version 4 Date: November 18, 2021

Clinicaltrials.gov Registration #: NCT04082884

Page 1 of 26

APPROVED BY THE YALE UNIVERSITY IRB 11/18/2021

HIC#: 2000026189

SECTION I: RESEARCH PLAN

- 1. **Statement of Purpose:** This prospective, open-label pilot/feasibility study of youth with T1D is to evaluate glycemic and metabolic changes taking place with a very low carbohydrate diet.
- 2.
- 3. **Probable Duration of Project:** The expected duration of the project is 5 years, including all follow-up and data analysis activities.
- 4. Background: As recently reported by the Type 1 Diabetes Exchange (T1DX) Registry, adolescents with type 1 diabetes (T1D) was the age group that had the highest hemoglobin A1c (A1c) levels compared to older participants; young adults aged 10-25 years were a close second (1). While the American Diabetes Association (ADA) recommends youth target A1c of <7.5% and adults <7%, only 17% of youth and 21% of young adults in the T1DX achieved these targets despite increased penetrance of diabetes technologies into clinical care (1, 2). These data suggest a need for novel approaches to improve glycemic control in adolescents and young adults with T1D.

Even for compliant youth with T1D, postprandial hyperglycemia continues to pose a challenge for many reasons, including, delayed insulin absorption and action compared to absorption of glucose from the gastrointestinal tract and dysregulated glucagon secretion after mixed meals (3). Moreover, postprandial glycemic changes can differ substantially depending on the macronutrient composition of the meal. Specifically, meals with reduced carbohydrate but increased fat and protein content will lessen immediate postprandial hyperglycemia (4). For many, being able to avoid carbohydrates and adhere to a very low carbohydrate diet may be easier than administering varying amounts of insulin for variable amounts of carbohydrate intake. Although standard treatment of T!D recommends varying the pre-meal dose of rapid-acting insulin depending on the patient's insulin to carbohydrate ratio, studies have shown that inaccurate carbohydrate counting happens frequently and contributes to increased glycemic variability (5).

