Research Plan: This prospective feasibility study of 10 youth (ages 13 – 25) with T1D will evaluate glycemic and metabolic changes after 2 weeks of a high protein VLCD compared to 2 weeks on a standard carbohydrate diet (see Table 1). The study will take place in 2 parts. Part 1 will only involve the high protein VLCD, but part 2 will involve high protein VLCD and high fat VLCD's.

| Type of Diet | Carbohydrates | Protein | Fat |
|-------------------|---------------|---------------|---------------|
| Standard | 25%+ | Not specified | Not specified |
| Carbohydrate | | | - |
| High Protein VLCD | 11% | 54% | 35% |
| High Fat VLCD | 11% | 23% | 66% |

Table 1. Types of study diets and macronutrient content in each planned diet.

Part 1: First, to evaluate the feasibility of following a high protein VLCD, participants will follow a standard carbohydrate diet for 2 weeks, followed by a 1 week transition to a VLCD, and then follow the a high protein VLCD for 2 weeks. The study will consist of 3 in person or virtual visits which will take place over ~5 weeks. All participants will be initially studied for 2 weeks while ingesting a standard diet recommended by the American Diabetes Association, followed by a 1-week transition to a VLCD, and followed by 2 weeks on the high protein VLCD. During the first (baseline) period fasting β -hydroxybutyrate levels will be measured 2-3 times per week. During the VLCD study periods, fasting β -hydroxybutyrate levels will be measured daily in the morning using a blood ketone meter; insulin doses will be collected using insulin pump downloads and continuous glucose monitoring (CGM) profiles will be used to assess glycemic excursions on each diet, as

[figure not shown]
Page **3** of **26**

well as the time in hypo-, eu- and hyperglycemic ranges. Part 1 of the study is anticipated to be complete by December 31, 2022.

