5. **Participants**: This study will enroll 10-20 participants (ages 13 to 25) with T1D. At least 4 adults over the age of 18 will be enrolled. Ten youth will be involved in Part 1, which evaluates feasibility of the diet. If those youth would like to continue to Part 2 of the study they may continue, or they will be replaced by new participants. To be eligible for inclusion, the participant must have T1D for at least 1 year, have an A1c between 6.5% to 10.0% inclusive, and BMI of at least 19 kg/m2 (or 5th percentile for those under age 18) and be willing to wear a CGM, which is the currently recommended standard of care for children with type 1 diabetes and is FDA approved for use above age 2 years. They must also be willing to adhere to a VLCD, measure β -hydroxybutyrate levels daily and to keep a detailed food diary. Participants who are unable to wear a CGM, monitor their diabetes control or maintain the VLCD will be replaced.

Study visits: Participants will be recruited from Yale Pediatric Diabetes Center and Yale Diabetes Center clinics, as well as through social media. All participants will undergo pre-screening of their electronic medical record (or faxed medical record from their pediatric endocrinologist or endocrinologist) to evaluate study eligibility by review of medical history, as well as prior physical exams and laboratory tests. No blood will be collected in part 1 of the study.

Figure 1. Timeline of visits and telephone follow ups for the duration of the study. Visits and calls may be modified depending on patient availability and academic schedule. Part 1 of the study will involve in-person or virtual visits (Facetime, Video Doximity Calls, Zoom, or Skype) and telephone study visits. Part 2 of the study will involve in-person visits.

Screening & Enrollment Visit 1: Screening will be conducted by invitation to potentially eligible subjects. For the first part of the study, the study will be explained and telephone or e-consent will be obtain prior to conducting any study procedures. Participants will 1) meet in person or 2)use telephone to discuss the study or 3) Skype, Zoom, FaceTime or Doximity Dialer enabling video calls. Scales will be provided for all participants.

Consent: Consent will be transitioned to an online/electronic format using the YSM version of REDCap if consent is not obtained in person.

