- Risks of Very Low Carbohydrate Diet: In order to minimize the symptoms associated with transitioning to a low carbohydrate diet abruptly, participants will be slowly transitioned over 1 week to help them acclimate and avoid unwanted symptoms.
- Hypoglycemia/Hyperglycemia: Participants will be contacted frequently during the course of the study. Blood draws will be done frequently during the HRU or CSRU admission to minimize hypoglycemia and hyperglycemia. Intravenous glucose will be available in case hypoglycemia occurs. All infusates containing insulin are prepared under a filtration cabinet (Laminated HLDA filter) by a qualified member of the research team using sterile disposable materials.
- Participants will be encouraged to monitor closely for signs of glycemic deterioration and will be able to contact our diabetes staff at any time if concerns arise.
- At the end of each visit, the participant will receive guidance for glucose monitoring, food intake, and insulin dosing as needed.
- During the study, insulin doses will be adjusted regularly (2-3 times per week as needed) to prevent hypoglycemia. Participants will use a real-time CGM that will provide alerts at the time of hypoglycemia and allow for early detection of hypoglycemia as well. Participants will be trained on treatment of hypoglycemia and to contact the study team immediately in any case of severe hypoglycemia.
- If any subject has 2 episodes of severe hypoglycemia, they will be transitioned to a regular diet after the 2nd episode of severe hypoglycemia.

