 - Percent time in range for sensor glucose values (70-180mg/dl)
 - Sensor-derived average glucose
 - % Time severe hypoglycemia (<55 mg/dL)
 - % Time hypoglycemia (<70mg/dL)
 - % Time hyperglycemia (>180mg/dl)
 - % Time severe hyperglycemia (>250 mg/dL)
- With respect to assessment of glycerol and glucose metabolism, we will use non-parametric paired ttest for comparison using a convenience sample for this pilot feasibility study.
- Descriptive differences between fasting ketone levels, insulin to carbohydrate ratios, insulin to protein ratios, insulin sensitivity factors, total daily insulin dose will also be reported.
- Glucagon, glucose, and beta-hydroxybutyrate response to arginine stimulation
- Questionnaires will evaluate changes in diabetes treatment satisfaction, nutritional knowledge, and diabetes distress over time. These analyses will help determine satisfaction with the study diet when compared to a standard diet. Due to the pilot nature of the study, these analyses will be exploratory, and we will not adjust for the number of comparisons.
- Meal content will be determined by using the ASA24 program (https://asa24.nci.nih.gov). Macronutrient content of each diet will be reported.
- Safety Analysis: Frequency of diabetic ketoacidosis and severe hypoglycaemia events will be assessed in all participants, including those whose data do not meet evaluability criteria.

HIC#: 2000026189

SECTION II: RESEARCH INVOLVING DRUGS, BIOLOGICS, RADIOTRACERS, PLACEBOS AND DEVICES

If this section (or one of its parts, A or B) is not applicable, check off N/A and delete the rest of the section.

- A. RADIOTRACERS
- B. DRUGS/BIOLOGICS
- 1. If an **exemption from IND filing requirements is** sought for a clinical investigation of a drug product that is lawfully marketed in the United States, review the following categories and complete the category that applies (*and delete the inapplicable categories*): **N/A**

2. **Background Information:** All substances are non-radioactive and have been extensively used in pediatric research in the last 15 years by our team with no side effects or adverse effects. Recent studies involving minors using glucose and glycerol isotopes performed by members of our research team are listed below.

| HIC # | Age group | Isotope | Dosage | Isotope | Dosage |
|------------|------------------|---|----------------------------|---------------------------------------|-------------------------|

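### Part 1 tests whether the very low carbohydrate diet can be followed, but those who cannot maintain it are replaced and no count of starters, completers, stops or replacements is planned

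*Combined protocol and SAP*

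**What the plan says.** The Statement of Purpose describes the trial as follows: "This prospective, open-label pilot/feasibility study of youth with T1D". It names glycemic and metabolic change as what will be evaluated. The Research Plan gives Part 1 its own task: "First, to evaluate the feasibility of following a high protein VLCD". Section I, 5 repeats this: "Ten youth will be involved in Part 1, which evaluates feasibility of the diet".

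Two rules deal with people who come off the diet. Section I, 5 states: "Participants who are unable to wear a CGM, monitor their diabetes control or maintain the VLCD will be replaced". No cap on replacements is given, and nothing says how a replaced person is to be reported. Separately, under Minimizing Risks in Section I, 11: "If any subject has 2 episodes of severe hypoglycemia, they will be transitioned to a regular diet". That rule does not say whether the person is then replaced.

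Section 13 lists these results:
- sensor glucose summaries and paired tests;
- glucose and glycerol metabolism;
- ketone and insulin descriptives;
- the arginine response;
- questionnaires;
- diet composition ("Macronutrient content of each diet will be reported");
- a safety analysis of ketoacidosis and severe hypoglycaemia, of which it says: "severe hypoglycaemia events will be assessed in all participants, including those whose data do not meet evaluability criteria".

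It lists no completion, discontinuation or replacement result and no feasibility criterion.

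**The concern.** In a study of whether a diet can be followed, failure to follow it is the outcome of interest. Here that failure triggers replacement, and no planned result records it. Once the ten places are filled by people who maintained the diet, the final group looks the same whether nobody or several others dropped out on the way. Section 11 names nausea, abdominal pain and fatigue among the diet's possible effects. Someone who gives up for such a reason, without ketoacidosis or severe hypoglycaemia, would appear in no planned count. At stake is whether Part 1 can report an answer to its own question.

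**Working it through.** **The plan's own figure.** There is none to reproduce. The plan gives no expected completion rate, dropout allowance or number of replacements, and it describes its sample as one of convenience. The inputs are therefore the ten places in Part 1 (Section I, 5) and assumed values for the rest.

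**Step 1: does any planned result give completion?** Each nearby item in Section 13 was checked for a numerator (people who finished) and a denominator (people who started).
- Safety analysis: covers all participants, but counts ketoacidosis and severe hypoglycaemia events, not diet stops.
- Diet composition: describes intake, not who started or finished.
- Questionnaires: describe satisfaction, nutrition knowledge and distress among those who answer.
- Sensor glucose comparisons: paired, so they need data on both diets.

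The investigator's adverse event review in Section 12 also concerns events. None of these gives a completion rate.

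**Step 2: what could go unseen?** Suppose ten people maintain the diet and k others were replaced. Completion among starters is 10/(10 + k). The intervals are exact (Clopper-Pearson) 95%.

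| k replaced (assumed) | Completed / started | Completion | 95% CI |
|---|---|---|---|
| 0 | 10/10 | 100% | 69% to 100% |
| 1 | 10/11 | 91% | 59% to 99.8% |
| 2 | 10/12 | 83% | 52% to 98% |
| 3 | 10/13 | 77% | 46% to 95% |
| 5 | 10/15 | 67% | 38% to 88% |

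In every row the final group consists of the same ten completers.

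**Step 3: is replacement likely to arise?** Let p be the assumed share of starters who can maintain the diet. The chance that at least one of the first ten cannot is 1 − p^10. The mean number replaced before ten places are filled is 10(1 − p)/p.
- p = 0.9: 1 − 0.9^10 = 65%; 10 × 0.1/0.9 = 1.1 replaced.
- p = 0.8: 1 − 0.8^10 = 89%; 10 × 0.2/0.8 = 2.5 replaced.
- p = 0.7: 1 − 0.7^10 = 97%; 10 × 0.3/0.7 = 4.3 replaced.

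Even if nine in ten starters can maintain the diet, at least one replacement is more likely than not.

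**The case against.** The best defence is that feasibility is not the only purpose. The Statement of Purpose and the Aims are about glycemic and metabolic change, and the Aims name no feasibility endpoint. Replacing people to obtain ten paired glucose records suits that purpose. Adherence is reviewed by telephone three times a week from food diaries and photographs, so the information will exist. Diet composition and satisfaction also bear on whether the diet is workable. All of this stands. It makes the omission easy to repair, but it does not put a completion result into the plan, and the Research Plan and Section I, 5 do give Part 1 a feasibility role.

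Four stronger readings are tempting, and the documents do not support them.
- A reader might infer that the two-episode safety stop leads to replacement. The text never links the two rules; a stopped participant can be read as unable to maintain the diet, but need not be.
- A reader might infer that the stop rule biases the hypoglycaemia comparison. The plan gives no event rate and does not say what happens to a stopped participant's data, so no bias of any size can be established.
- A reader might infer that replaced people vanish from the study. They do not: the safety analysis retains all participants for ketoacidosis and severe hypoglycaemia.
- A reader might infer that the plan will claim ten completers out of ten. It proposes no completion figure at all, and that is the gap.

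**Conclusion.** The point holds as an omission that is cheap to repair. Part 1 has a feasibility task, the replacement rule removes from the final group the people who bear on it most directly, and Section 13 plans nothing that would show how many there were. With 1 to 5 people replaced, completion among starters would be 91% down to 67% without appearing in any planned result. Those counts, and the values of p, are assumptions; the size depends on them, but the absence of the result does not. The glycemic and metabolic analyses can go ahead as planned.

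Two gaps nearby need clarification only. A severe hypoglycemia episode is not defined (the 55 mg/dL figure labels a percent-time sensor outcome), and the evaluability criteria are mentioned without being stated.

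**What to change.** **Section 13.** Add a feasibility result for Part 1: the number who start the transition week, complete two weeks on the VLCD, stop (with reason, listing the two-episode safety stop separately) and are replaced. Give the completion proportion with an exact 95% confidence interval, using everyone who starts the transition as the denominator.

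**Section I, 5.** After the replacement rule, add that replacements may be enrolled to fill the ten pairs of sensor records, but that replaced participants stay in the feasibility denominator.

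**Secondary clarification.** Define the severe hypoglycemia episode and state the evaluability criteria.

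**Cost.** One more descriptive analysis, one sentence on replacement and the definitions. No extra visits, sensor wear or participants are needed, because the counts come from enrolment and follow-up records the study will hold anyway. The downside is that the completion figure may be less favourable, and with 10 to 15 starters its interval will be wide.

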- ii. If requesting a waiver of signed authorization, describe why it would be impracticable to obtain the subject's signed authorization for use/disclosure of this data: Some potential subjects may call or email after learning about the trial by word of mouth. We can ask some basic screening questions about age, date of diagnosis etc. before scheduling an enrollment visit to do further screening to determine study eligibility.

Page 20 of 26

The investigator assures that the protected health information for which a Waiver of Authorization has been requested will not be reused or disclosed to any person or entity other than those listed in this application, except as required by law, for authorized oversight of this research study, or as specifically approved for use in another study by an IRB.

Researchers are reminded that unauthorized disclosures of PHI to individuals outside of the Yale HIPAA-Covered entity must be accounted for in the "accounting for disclosures log", by subject name, purpose, date, recipients, and a description of information provided. Logs are to be forwarded to the Deputy HIPAA Privacy Officer.

- 6. Process of Consent/Assent: Potential participants who express interest in the study will be given a copy of the Consent Form/Parent Permission/Assent Form, asked to review, and then given the opportunity to discuss the study with the investigators in detail. For part 1 of the study, consent will be performed over the phone or virtually. This will be done either via RedCap or by emailing/mailing the consent form and having the participant email/mail the signed consent form back to the researcher. For part 2 of the study, consent will take place in person. The investigator will comply with all applicable regulatory and legal requirements, ICH GCP guidelines and the Declaration of Helsinki in obtaining and documenting the informed consent. It will of course be stressed that participation is voluntary, and non-participation will not affect continuing care at the Yale Children's Diabetes Program. The participant will have the right to refuse to participate or to withdraw at any time.

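### Replacing participants who cannot maintain the VLCD, with evaluability left undefined, puts the paired CGM comparisons at risk of selection bias, probably in the diet's favour for time in hypoglycaemia

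*Combined protocol and SAP*

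**What the plan says.** Section I, item 5 (Participants) sets the Part 1 size, "Ten youth will be involved in Part 1, which evaluates feasibility of the diet", and the replacement rule: "Participants who are unable to wear a CGM, monitor their diabetes control or maintain the VLCD will be replaced". It does not say what happens to CGM data already collected from someone who is replaced.

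Section I, item 13 (Statistical Considerations) compares the diets by paired t-test in both parts. The measures are time in range, mean glucose, and time below 70, below 55, above 180 and above 250 mg/dL. It names no analysis set, minimum CGM wear or missing-data rule. Its last bullet counts diabetic ketoacidosis (DKA) and severe hypoglycaemia in all participants, "including those whose data do not meet evaluability criteria". Those criteria are defined nowhere.

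Two other places bear on who has VLCD data. Under Minimizing Risks (Section I, item 11): "If any subject has 2 episodes of severe hypoglycemia, they will be transitioned to a regular diet after the 2nd episode of severe hypoglycemia". Under Process of Consent/Assent (Section III, item 6): "The participant will have the right to refuse to participate or to withdraw at any time". Neither says how CGM data before or after the change are used.

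**The concern.** The safety bullet needs to mention people who fail evaluability only if the other analyses leave them out. Together with the replacement rule, the natural reading is that the CGM tests use participants who completed the VLCD, topped up until there are ten.

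That selection can depend on the outcome. The study is open-label (Section I, item 1). The calls that assess adherence, three a week, also upload and review CGM data (Section I, item 5, enrolment visit). Whether someone cannot maintain the diet is therefore judged with their glucose in view and no written criterion.

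Part 1 has a single sequence: standard diet, transition week, VLCD. A participant lost during the standard-diet weeks has not yet shown a response to the VLCD, so that loss cannot select on the response. A participant lost on the VLCD can be lost because of it. The hypothesis in item 4 is more time in range through less time above 180 and below 70 mg/dL. Losing those who did badly on these measures would move the result toward it, and nothing in the plan would label the result as applying to completers only.

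**Working it through.** The documents give no power, alpha, effect size, SD or dropout rate, so there is no planned figure to reproduce. The check has two parts, and every rate in it is an assumption.

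**1. Shift from replacing poor responders**

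Inputs:
- n = 10 pairs (item 5).
- True mean difference zero, normal paired differences, two-sided 5% t-test (assumed).
- A fraction q of starters, those tolerating the diet worst, leave and are replaced until ten complete, and the leavers' CGM is not used (assumed).
- Tolerance has correlation ρ with glycaemic response (assumed).

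One replacement on the way to ten completers is 1/11 = 9% of starters, and two are 2/12 = 17%. So q = 10-20% corresponds to roughly one or two people.

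Shift in favour of the diet, in SDs of the paired difference = ρ × φ(z_q) / (1 − q), where z_q is the q-quantile of the standard normal.
- q = 10%: 0.1755 / 0.9 = 0.195, so ρ = 0.3 gives 0.058 and ρ = 0.6 gives 0.117.
- q = 20%: 0.2800 / 0.8 = 0.350, so ρ = 0.3 gives 0.105 and ρ = 0.6 gives 0.210.

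Probability of a significant result favouring the diet when there is no effect (40,000 simulated trials per cell):

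| q | ρ = −0.3 | ρ = 0 | ρ = 0.3 | ρ = 0.6 | ρ = 1 |
|---|---|---|---|---|---|
| 10% | 1.6% | 2.6% | 3.6% | 5.2% | 6.9% |
| 20% | 1.2% | 2.5% | 4.9% | 8.9% | 19.4% |

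The nominal value is 2.5%, and the 2.6% is simulation error. The ρ = 1 column means removal exactly by outcome, which no rule in the protocol does. It is an outer bound.

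For scale, the standard error of the mean difference with ten pairs is 1/√10 = 0.316 SD. The shift of 0.058-0.210 SD is therefore 0.058/0.316 = 0.18 to 0.210/0.316 = 0.66 standard errors. With an assumed SD of 10 percentage points for the change in time in range, it is 0.6 to 2.1 points.

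**2. How often the two-episode stop would act**

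Assume severe hypoglycaemia occurs independently at r events per person-year over the transition week plus the 2-week VLCD. Then λ = 3r/52, the chance of two or more events is 1 − e^(−λ)(1 + λ), and the chance that any of ten participants reaches two is 1 − (1 − that)^10.
- r = 0.1: 0.0017% per person, about 0.02% for any of ten.
- r = 1.0: 0.16% per person, about 1.6% for any of ten.

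This route is minor next to replacement and evaluability. Where it does occur, the question is one of labelling: the participant returns to a regular diet, and nothing says whether later CGM readings inside the scheduled VLCD weeks count as VLCD.

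**The case against.** The strongest objection is that exclusion is inferred. The replacement sentence is an enrolment rule, the stopping rule changes a diet, and the safety bullet protects safety counts. A reader might infer that the plan removes people who do badly on the diet and that its CGM results are therefore biased. The text does not say that. It also does not say that their data are kept, so the choice could be made after the data are seen. That part of the point survives.

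Direction is also not settled for every measure. Someone who leaves because of hypoglycaemia may have had lower mean glucose and less time above 180 mg/dL, so losing them could move those measures against the diet. Counting regular-diet readings as VLCD time would dilute a real fall in hyperglycaemia. Inability to wear a CGM or to monitor control can arise in the standard-diet weeks too, and need not track the response to the VLCD. All this stands and limits the claim.

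A reader might extend the point to a biased contrast between the two VLCD arms in Part 2. Item 13 plans only paired tests and specifies no between-arm comparison, so no stated analysis is affected in that way. Nor are the severe harms hidden: DKA and severe hypoglycaemia are counted in everyone, and the principal investigator reviews adverse events as each participant finishes.

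Finally, this is a pilot with no power claim, and item 13 describes the metabolic comparison as "using a convenience sample for this pilot feasibility study". That lowers the stakes. But the plan does run significance tests on the CGM measures, and with ten pairs one or two substitutions matter.

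**Conclusion.** The concern holds as a risk of bias. The undefined evaluability criteria and the replacement rule together allow, and most naturally imply, a completers-only CGM comparison selected after exposure to the VLCD. The likely direction is toward the diet for time below 70 and 55 mg/dL. It is less certain for time in range and time above 180 mg/dL.

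With 10-20% replaced and ρ between 0.3 and 0.6, the shift is about 0.06-0.21 SD and false benefit is about 4-9% instead of 2.5%. These figures rest on an assumed replacement rate, an assumed correlation and full loss of the leavers' CGM data, none of which the documents give. If leaving is unrelated to glycaemia there is no bias, and if those doing better leave, it reverses. A reader might take the two-episode hypoglycaemia stop as the main mechanism, but at the assumed event rates it would seldom be met in about three weeks. The plan should be changed because the gap can be closed cheaply before the data are seen.

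**What to change.** Amend item 13 and the replacement sentence in item 5:

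1. Main CGM set: every participant who starts the 2-week VLCD period and meets one prespecified minimum amount of sensor data, whether or not later replaced. Set the minimum low enough to retain early leavers and apply it identically to both diet periods. This becomes the definition of evaluable. Replacements are added and displace no one.
2. VLCD-period readings run up to the day the participant leaves the diet. Later readings are not counted as VLCD.
3. The completers-only result is a sensitivity analysis, labelled as such.
4. Report the number, timing and reasons for every replacement, including those in the transition week.

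The clinical stopping rule is not changed.

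The cost is wording in two places and a diet-stop date on the case report form, since CGM is already worn and uploaded. Some participants will contribute fewer than 14 days, and a short record counts as much as a full one in the t-test, which is why a minimum is needed. Ending readings on the day of leaving may make the estimate slightly less favourable to the diet. Transition-week leavers have no VLCD-period data and stay outside the main set, so some selection remains; item 4 makes it visible.
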